We will recruit and randomly assign 300 families with middle school youths (6th and 7th grade) to one of three conditions: (a) web/mobile + coach intervention (n=100), (b) web/ mobile-only intervention (n=100), or (c) waitlist control group (n=100) that will receive middle school as usual and then offered the web/mobile-only intervention immediately after completing their final time point of data collection (12 months after enrollment). This design will enable us to compare outcomes associated with the web/ mobile-only intervention with a coach version. Participants will be randomly assigned to condition within school such that each school will have a similar number of participants in each of the three conditions. Participation in this study will be 12 months for all families, regardless of condition.

Families in all three conditions will be mailed a packet that includes a parent consent form, youth assent form, the parent and youth surveys, and 4 self-addressed, stamped envelopes so that each consent and survey may be mailed back separately to project staff. This “pre-assessment” includes standard, widely-used questionnaires that ask questions about the child's abilities and behavior, parenting practices, family dynamics, family demographics, family health behaviors, and life stressors and take about 30 minutes to complete. At the time of the pre-assessment, parents will also be asked to provide research staff with their driver's license number. We collect these because they assist us in relocating families for subsequent phases

of this longitudinal research project if they were to become lost. Our research team subscribes to a service which allows us to search for individuals by DL numbers to obtain a new address or phone number from items such as utility bills. Driver's license numbers will be retained for the duration of the research project. Participants will be assured that this information will be kept private, consistent with other data collected, and will be destroyed no later than 5 years after the end of the project.

One week after mailing this packet, a paid staff member will call the caregiver to see if the caregiver or youth have any questions about the consent form or the survey. If the family has not yet returned their surveys, they will be reminded to do so as soon as possible.

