Families in all three conditions will be invited to participate in follow-up questionnaires at 3 months, 6 months, and 12 months that will be identical to the pre-assessment so that we can evaluate change over time in the assessed constructs. The estimated time needed for parents and youth to complete each of these follow-up questionnaires is 30 minutes. At each of these three assessment points parents and youth will be mailed a questionnaire packet and return them independently to the research team in their own self-addressed stamped envelope. At the time of the 3-month follow up, parents in the two intervention conditions will also complete a 2-page Website Feedback Survey. These surveys will also be completed by mail.

All families will be compensated for their time. Each family will receive \$100 for completing assessments at baseline, 3 months, 6 months, and 12 months for a total of \$400. Because sustained family involvement in a longitudinal study is critical to maintain, families will be offered a \$50 bonus if they complete all 4 assessment points.

Unfortunately, the website is only offered in English. However, Spanish-speaking families at these schools will still be offered options to allow them to participate in the study and/ or receive the intervention if they desire. Spanish speakers who are comfortable reading English will be randomly assigned to one of the three experimental conditions described above, but will have an option to complete the pre-assessment and follow-up assessments in either English or Spanish (and the website in English). Those who are not comfortable reading English will still be offered the opportunity to participate and be compensated, but will be assigned to a **nonexperimental tele-health condition** described below. All of the information available online in the parenting skills modules has been translated into Spanish and will be presented to these families via pamphlets.

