For the **web/mobile + coach condition**, a coach will contact the parent for an initial phone session after they have logged into the website for the first time to conduct an "initial interview" over the phone. The initial interview will set the stage for the assessment and intervention and motivate parents to engage in the program. Parents will then be directed to complete the online assessment, which is identical to the one used in the web/ mobile only condition. After completing the assessment, parents will view the feedback online, with either phone or video conferencing support from the coach, who will be using motivational interviewing to provide feedback on both strengths and areas of growth based on the assessment. The coach will help parents set goals in terms of intervention targets and will then arrange to check in with the parent another 2-5 times about their progress. The first check-in will occur after one skills session of the online parenting curriculum has been completed, or after 2 months, whichever comes first. Families may then contact the coach by posting a question or concern online in an "ask the expert" format. The coach will respond within 24 hours via text, email, or phone. Additional meetings may be scheduled as needed.

The **nonexperimental tele-health condition has been developed for Spanish-speaking populations** and is somewhat similar to the web/mobile +coach condition. Participants in this condition will complete pre-assessments and follow-up assessments in Spanish, and will receive a tele-health version of the intervention via mail and phone communication with a Spanish speaking coach. Over the phone, a Spanish speaking coach will provide feedback to the parents on the data that they provided, and suggest areas for skill development. The family and coach will decide together which areas they want to work on, and the coach will mail the relevant pamphlets to the family. The coach and family will continue to meet over the phone as desired to make progress towards the parents' goals.

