After the feedback, a menu of options tailored for the family and based on the assessment will be presented to families in **both treatment conditions**. These options, described below under "Content of follow-up sessions" will be Skills Sessions-guided by our Everyday Parenting curriculum. The Skills Sessions will be delivered online to both treatment conditions and consist of content and structured activities that are designed to help parents learn each skill. In the **web/mobile+ coach condition**, a coach will check in with parents to assess progress and support gains in positive behavior. In the **web/mobile-only condition**, parents will complete the Skills Sessions at their own pace without these check-ins. Parents in either of these conditions may log in to the website as many times as they like to learn more or participate in any of the other Skills Sessions.

After completing the FCU, families will continue to participate in the post-tests previously described. These post-tests occur at 3, 6, and 12 months after the pre-assessment. At the end of the 3 month post-test assessment, parents will also be asked to complete a Website Feedback Survey. This questionnaire will assess satisfaction with the content and delivery of the model and factors related to uptake and usage of the information. This questionnaire will be mailed to participants along with the 3 month post-test. It should take about 10 minutes to complete.

Content of Skills Sessions and Web/Mobile Activities. On the basis of assessment results, parents will be offered a variety of follow-up parenting skill activities. Each of the following Skills Sessions, derived from our Everyday Parenting curriculum (Dishion et al., 2011), will include content that is animated, video based, and interactive. They will each include activities for tracking of behavior and will provide ongoing feedback to parents on their success. Each Skills Session will also highlight behaviors that target school success at this age, including homework completion, attendance, and home-to-school planning.

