Potential risks are minimal and include possible psychological or emotional risks and information risks involving breach of confidentiality.

Psychological or emotional risk. Participants may feel some discomfort completing questionnaires that ask questions about their child's development and family stress and well-being. Some participants may view the questions as minimally intrusive. Participants in the focus group will be asked to maintain confidentiality, but we cannot guarantee that they will not disclose information outside of the focus group. Participants in the web/mobile + coach condition may feel shy or embarrassed when participating. To minimize these risks, participants will be assured that their participation is voluntary and they may skip any questionnaire item(s) they are uncomfortable with. All participants may request discontinuation of any procedure at any time if they experience undue distress. Consent forms will include contact information for our project coordinator, [name]. Should parents/caregivers or children experience an adverse reaction to the assessments and require medical or psychological assistance, they may contact [name], who will evaluate the situation and, if necessary, contact the PI, a licensed psychologist, to make appropriate referrals.

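### Adverse events as such are neither elicited nor tabulated: the one described reporting route is family-initiated and worded for the assessments, and unequal staff contact makes spontaneous reports non-comparable across arms

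*Protocol*

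**What the plan says.** Three parts of the Protocol and one of the SAP bear on this.

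- **Risks and response (Protocol, Section G, psychological or emotional risk).** The paragraph lists discomfort with the questionnaires and also a discomfort from the intervention: "Participants in the web/mobile + coach condition may feel shy or embarrassed when participating". The response to an adverse reaction is: "Should parents/caregivers or children experience an adverse reaction to the assessments and require medical or psychological assistance, they may contact" the project coordinator, "who will evaluate the situation and, if necessary, contact the PI, a licensed psychologist, to make appropriate referrals". A broader sentence stands just before it: "All participants may request discontinuation of any procedure at any time if they experience undue distress". The consent forms are said to carry the coordinator's contact details.
- **Data collection (Section C, Main Research Study).** All three arms receive "follow-up questionnaires at 3 months, 6 months, and 12 months that will be identical to the pre-assessment". The one addition is a Website Feedback Survey at 3 months, for parents in the two intervention arms, on satisfaction, uptake and usage.
- **Staff contact (same section).** A coach family has an initial call and supported feedback, after which the coach "will then arrange to check in with the parent another 2-5 times about their progress". An earlier paragraph of the section promises such families at least 2 scheduled phone sessions. For web-only families, "parents will complete the Skills Sessions at their own pace without these check-ins". Wait-list families are told that the next contact comes in 3 months.
- **Analysis (SAP, Data Analysis and Table 2).** Seven outcomes are compared in three contrasts, including conduct problems, hyperactivity and emotional problems. There is no adverse-event analysis.

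**The concern.** The response route is narrower than the risk list in its own paragraph. Read literally, distress from the program's feedback, a coach call or practice of a parenting skill does not meet the stated trigger. The route is also passive: it works only if a family decides to call, and it ends in evaluation and referral, with no log or tabulation described.

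Passive reporting is least trustworthy when arms differ in how often staff talk to families, as they do here by design. Reports would tend to come from the coach arm because that is where conversations take place. The Protocol (Aim 2) values the web-only version because it needs no coach and could be disseminated widely. That arm has the weaker means of bringing a problem to light, so an absence of reports from it would carry little information.

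**Working it through.** The plan states no figure on harms, so there is none to reproduce. The check sets the texts side by side and then adds a labelled illustration.

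**1. Trigger against risk list (Section G).** Listed sources of discomfort: questionnaires, the coach condition, and focus-group disclosure. Trigger of the adverse-reaction route: the assessments. The coach condition appears in the first list and not in the second.

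**2. What is asked.** Section C describes the mailed questionnaire as covering the child's abilities and behavior, parenting, family dynamics, demographics, health behaviors and stressors. No item on harm from taking part is described. The Website Feedback Survey is described as covering satisfaction and use, and it goes to parents only.

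**3. Scheduled staff contact between randomization and the 3-month packet.**

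| Arm | Contact described |
|---|---|
| Web plus coach | Begins after first login, unless the family makes contact first; at least 2 scheduled phone sessions, more under the intervention description; an online question channel answered within 24 hours |
| Web-only | Login email; computer-generated feedback; no check-ins |
| Wait-list | Thank-you email; next contact at 3 months |

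**4. What the outcome scores do show.** Simple change in observed means, pretest to 1 year, from the labelled rows of SAP Table 1 (a higher score is taken to mean more problems):

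- Hyperactivity: wait-list 3.46 − 3.45 = +0.01; web-only 3.21 − 3.72 = −0.51; coach 3.41 − 4.19 = −0.78.
- Emotional problems: wait-list 2.60 − 2.34 = +0.26; web-only 2.64 − 2.56 = +0.08; coach 2.09 − 2.78 = −0.69.

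Table 2, wait-list versus web-only: conduct problems 0.04 (p = .236, analysed after a log transformation), hyperactivity −0.17 (p = .599), emotional problems 0.06 (p = .867). A large average worsening would therefore be visible by arm. Means do not show which families deteriorated, who needed help, or whether the program was the cause. Family conflict, a primary outcome in Aim 2.1 of the Protocol, has no row in Table 2.

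**5. Illustration of unequal capture (all rates assumed; the documents give none).** Let the true harm rate be 10% in two arms of n = 100, with 80% of harms surfacing in the coach arm and 40% or 20% in a less-contacted arm. Observed rates are 0.10 × 0.80 = 8% against 0.10 × 0.40 = 4% or 0.10 × 0.20 = 2%. The chance that a two-sided 5% test declares a difference, with p̄ the mean of p1 and p2, is approximately

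Φ{ [ |p1 − p2| − 1.96 √(2p̄(1 − p̄)/n) ] / √(p1(1 − p1)/n + p2(1 − p2)/n) }.

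- 8% vs 4%: (0.04 − 1.96 × 0.0336)/0.0335 = −0.77, giving 22%.
- 8% vs 2%: (0.06 − 1.96 × 0.0308)/0.0305 = −0.01, giving about 50%.

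For true rates from 5% to 20% and the same two capture pairs, the result runs from 13% (4% vs 2%) to 81% (16% vs 4%), although the arms do not truly differ. The normal approximation is rough at such small counts.

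**6. What asking everyone would deliver.** By the same formula with equal and complete enquiry, power at 100 per arm is 27% for 5% vs 10%, 51% for 10% vs 20%, 66% for 5% vs 15% and 90% for 5% vs 20%. Solicited answers would be mainly descriptive.

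**The case against.** The strongest reply is that the trial does collect comparable data on deterioration. The follow-up questionnaires are identical in all arms, and the SAP contrasts three problem scales between arms. That stands. A reader might infer that harm is never asked about, or that nothing about it can be compared across arms. The documents do not support either: average worsening is both measured and compared. What they lack is enquiry about events, need for help and attribution.

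A second reply is that a distressed family is not without recourse. Anyone may stop any procedure, the coordinator's details are on the consent form, and the word assessments could be read to include the online Family Check-Up assessment, which is part of the intervention. This is fair as to recourse. But these provisions also depend on the family acting, and none of them is a recording route.

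Third, the gap in contact should not be overstated. Coach sessions depend on the family logging in or reaching out, and the firm commitment is at least 2. A larger count assumes full engagement. The direction of the imbalance is unaffected.

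Fourth, a reader might count wait-list families as exposed without follow-up, because they are "offered the web/mobile-only intervention immediately after completing their final time point of data collection". The Protocol limits participation to 12 months for all families, so this is an offer of access after the study and not a gap in it.

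Fifth, timing. At the March 2019 Protocol, Cohort 1 was complete. If enrolment ended with the 2017-2018 school year, mainly 12-month packets of Cohort 2 were still to be sent. The SAP of July 2020 already reports 1-year results. This limits what a new sheet can yield in the main trial, but Phase 5 had not begun at that Protocol version.

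Finally, one Protocol page, the consent forms and the attached surveys were not available for review, so a provision there cannot be excluded.

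**Conclusion.** The point holds in this form: in the supplied text, adverse events as such are not elicited or tabulated; the only described adverse-reaction route is passive and worded for the assessments; and scheduled contact differs by arm. Spontaneous reports would therefore be incomplete and not comparable. The by-arm signal on harm is limited to mean outcome scores.

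The documents supply no event count, harm rate or capture rate, so no size of bias follows from them. The 13% to 81% range shows only that unequal capture can create a false difference under the stated assumptions, and the conclusion does not depend on it. Nor do the documents suggest that harm occurred: the Protocol classes the risks as minimal. The matter is an inexpensive improvement to what the trial collects and can say about harm. It does not undermine the efficacy contrasts.

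**What to change.** 1. **Reconcile Section G with itself.** Word the adverse-reaction route so that it covers the assessments and any part of the intervention, in line with the risks that the paragraph lists.
2. **Ask everyone the same question where mailings remain.** For Cohort 2 packets not yet sent at this Protocol version, in all three arms, add one separate, identically worded sheet. It asks parent and youth whether taking part caused distress or family problems and whether help was needed. Positive answers go to the existing contact. The outcome questionnaire itself stays unchanged. Add the same question to the Phase 5 parent end-of-study survey, since that phase collects no baseline or follow-up questionnaires.
3. **Report it.** Tabulate solicited answers descriptively by arm. For assessments already completed, state that harms were captured only by self-initiated report and that such reports cannot be compared across arms. If all mailings have gone out, this statement is the part of the fix that remains for the main trial.

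Cost: a Protocol amendment, one page in existing mailings, one descriptive table, about a minute of extra response time, and a few answers for existing staff to follow up. No visits or staff are added.

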Official Title: Prevention of Substance Use in At-Risk Students: A Family-Centered Web Program

NCT Number: NCT03060291

Document Date: July 14, 2020

Statistical Analysis Plan with Results Information

Data Analysis

Preliminary analyses included descriptive statistics and plots to screen outcomes for normality. Chi-square statistics and one-way ANOVA models were used to compare study condition and demographic characteristics between participants who dropped out of the study versus those who completed all four assessments.

Intent-to-treat analyses of condition effects were evaluated with mixed effects growth models using SAS 9.2 PROC MIXED and estimated using full-information maximum likelihood, an unstructured variance and covariance matrix, and random intercepts and slopes. Variability in outcomes from pretest to 1-year follow-up was modeled as a function of condition, time (coded in months), and a condition \times time interaction term. The intercept was specified at the 1-year follow-up assessment; thus, the condition effect is a test of whether intervention groups differed at the end of the study. Following Singer and Willet (2003), when constructing the longitudinal model we (a) examined empirical growth plots; (b) fit an unconditional means model; (c) fit an unconditional linear growth model; (d) fit unconditional non-linear models; and (e) compared models of longitudinal change using the Akaike Information Criterion. Three a priori dummy coded comparisons were examined: wait-list control (reference group) versus web-only, wait-list control (reference group) versus web plus coach, and web-only (reference group) versus web plus coach. Effect sizes for the condition effect at the end of the study are reported as Cohen's d (Cohen, 1988) and computed as model estimated differences in the outcomes at 1-year follow-up divided by the observed baseline pooled standard deviation.

Results

Preliminary analyses. Demographic make-up of the sample, program use metrics, baseline equivalency of the three intervention groups, and correlations of the pretest measures

have been previously reported (Stormshak et. al., 2019). Briefly, parents in the study were predominately female, on average 40.0 ($SD = 6.1$) years of age, and 35% had a 4-year college degree or graduate training. The children in the study were approximately gender balanced, mostly white, and mostly lived in suburban environments. Use of the site was robust, but the web plus coach group used the program significantly more than the web-only group. Participants in the three conditions did not differ on gender, area (rural, suburban, urban), minority status, SES risk score or pretest measures of the outcomes indicating randomization produced initially equivalent groups. The correlations of the pretest measures ranged from $r = -.67$ to $r = .60$ (mean $|r| = .30$).

The outcomes approximated normal distributions except conduct problems which was normalized with a logarithmic transformation. Complete data was available for 88% of the sample and attrition was 6% at posttest, 8% at 6-month follow-up and 9% at 1-year follow-up. Number of assessments completed was not significantly associated with study condition, child's gender and child's race (all p -values $> .08$). Comparison of linear and non-linear unconditional models showed a linear model had superior fit to a linear and quadtric model for all study outcomes.

Table 1 provides means and standard deviations for the outcomes at each assessment point for each of the three conditions. Table 2 provides a summary of the condition effects from the growth models for the three a priori comparisons and is a test of whether groups differed in change in outcomes from pretest to the 1-year follow-up. No statistically significant (at $p < .017$) differences were found, although one trend-level effect ($p < .10$) is worth noting. The web plus coach group showed trend level differences in sense of parenting importance that favored the

web plus coach group relative to the wait-list control group, a small to medium effect (p -value = .081, $d = .28$), a small to medium effect (Cohen, 1988).

	Pretest		3-Month Posttest		6-Month Follow-up		1-Year Follow-up	
	M	SD	M	SD	M	SD	M	SD
Wait-list control	1.05	1.38	1.24	1.54	1.00	1.44	1.08	1.45
Web-only intervention	1.37	1.81	1.32	1.63	1.17	1.57	1.19	1.40
Web plus coach intervention	1.44	1.65	1.30	1.55	1.12	1.54	1.21	1.60
Hyperactivity								
Wait-list control	3.45	2.69	3.31	3.43	3.24	2.32	3.46	2.56
Web-only intervention	3.72	2.46	3.20	2.02	3.11	2.39	3.21	2.10
Web plus coach intervention	4.19	2.87	3.47	2.39	3.45	2.37	3.41	2.47
Emotional problems								
Wait-list control	2.34	2.27	2.56	2.42	2.47	2.30	2.60	2.37
Web-only intervention	2.56	2.28	2.36	2.23	2.45	2.37	2.64	2.43
Web plus coach intervention	2.78	2.12	2.20	1.97	2.31	2.04	2.09	1.96
SD = standard deviation.								

Table 2

Condition Parameter from Growth Models

Contrast and Outcomes	Estimate	SE	t-value	p-value	d
Wait-list control vs. Web-only					
Effortful control	0.07	0.12	0.60	.549	0.08
Sense of parenting importance	0.03	0.05	0.62	.535	0.09
Sense of parenting confidence	0.11	0.08	1.45	.149	0.19
Parenting self-efficacy	0.06	0.10	0.60	.547	0.08
Conduct problems	0.04	0.04	1.19	.236	0.16
Hyperactivity	-0.17	0.32	-0.53	.599	-0.07
Emotional problems	0.06	0.33	0.17	.867	0.02
Wait-list control vs. Web plus coach					
Effortful control	-0.02	0.13	-0.18	0.854	-0.03
Sense of parenting importance	0.08	0.04	1.75	0.081	0.28
Sense of parenting confidence	0.10	0.08	1.27	0.207	0.19
Parenting self-efficacy	0.06	0.10	0.56	0.575	0.08
Conduct problems	0.05	0.04	1.47	0.142	0.20
Hyperactivity	0.22	0.34	0.64	0.523	0.08
Emotional problems	-0.47	0.30	-1.53	0.127	-0.21
Web-only vs. Web plus coach					
Effortful control	-0.09	0.12	-0.73	0.469	-0.09
Sense of parenting importance	0.05	0.05	1.05	0.295	0.17
Sense of parenting confidence	-0.01	0.08	-0.16	0.871	-0.02

Contrast and Outcomes	Estimate	SE	t-value	p-value	d
Parenting self-efficacy	0.00	0.10	0.05	0.964	0.01
Conduct problems	0.01	0.04	0.24	0.810	0.03
Hyperactivity	0.36	0.32	1.15	0.252	0.14
Emotional problems	-0.51	0.31	-1.65	0.101	-0.22

Note. *SE* = standard error, *d* = d-statistic.
